6.4.2.3 Time to Symptomatic Progression

TTSP is defined as the time from date of randomization to date of assessment of ECOG performance status ≥ 2 with or without tumor progression based on investigator assessment. Deterioration in performance status is to be confirmed at one subsequent evaluation 8 weeks later. The first date at which the ECOG performance status was ≥ 2 will be used as the end date in the TTSP analysis (assuming the next subsequent visit confirmed the deterioration).

TTSP (Months) = (Date of ECOG ≥ 2 – Date of Randomization + 1)/30.4375.The censoring is performed as follows:

- If a patient does not have a post baseline ECOG performance status, then the TTSP will be censored at the randomization date;
- 2) If a patient has post baseline ECOG assessment but did not have ECOG ≥2 then TTSP will be censored at the last post baseline ECOG performance status assessment date.

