#### 10.2.3.2 SECONDARY ENDPOINT STATISTICAL ANALYSIS PLAN

For secondary efficacy endpoints, each comparison between treatment groups will be conducted at the final analysis with α=0.05 (two-sided). Secondary study endpoints will be analyzed only at the final analysis to determine the statistical significance, if any between, the Treatment and Control groups.

- Time to progression (TTP) will be calculated as the interval between the randomization date and the date of first disease progression as defined by the respective criteria noted below, death for any cause or of last contact for patients alive. The Kaplan-Meier method will be used to estimate the TTP curves in the two treatment arms; comparison between the curves will be performed using the log-rank test. Median TTP will be reported. Progression will be assessed separately using:
  - RECIST v1.1 criteria
  - mRECIST criteria
  - EASL response criteria (assessed bidimensionally on enhancing tissue)
- Time to symptomatic progression (TTSP) will be calculated as the interval between the randomization date and symptomatic progression, defined as assessment of ECOG performance status ≥2 with or without tumor progression based on imaging. Deterioration in performance status is to be observed at one subsequent evaluation 8 weeks later. For subjects who had not progressed symptomatically at the time of analysis, TTSP will be censored at their last date of PS assessment. The Kaplan-Meier method will be used to estimate the TTSP curves in the two treatment arms; comparison between the curves will be performed using the log-rank test. Median TTSP will be reported.
- Tumor response rate. The response probability will be estimated in each of the two treatment arms as proportion of CR+PR over the total number of ITT or PPP patients. The disease control rate (ie, CR+PR+SD) will also be compared between the treatment arms. The minimum time between image acquisitions is 6-8 weeks. Tumor response rate will be assessed separately using:
  - RECIST v 1.1
  - mRFCIST
  - EASL

Tumor response will be compared using the continuity adjusted Newcombe-Wilson test, and the 95% confidence limits will be calculated

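### TTSP requires ECOG ≥2 to be confirmed 8 weeks later, but the SAP has no rule for death before that check; by default these patients are censored, often on the day they deteriorated

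*SAP*

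**What the plan says.** SAP 6.4.2.3 runs TTSP from randomization to the "date of assessment of ECOG performance status ≥ 2 with or without tumor progression based on investigator assessment". It then requires confirmation: "Deterioration in performance status is to be confirmed at one subsequent evaluation 8 weeks later". The first ECOG ≥2 date is the event date only on a condition: "assuming the next subsequent visit confirmed the deterioration".

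Two censoring rules follow:

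- Rule 1: "If a patient does not have a post baseline ECOG performance status, then the TTSP will be censored at the randomization date".
- Rule 2, which uses the last post-baseline ECOG date: "If a patient has post baseline ECOG assessment but did not have ECOG ≥2 then TTSP will be censored".

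Protocol 10.2.3.2 has the same confirmation requirement ("Deterioration in performance status is to be observed at one subsequent evaluation 8 weeks later") and a broader censoring rule: "For subjects who had not progressed symptomatically at the time of analysis, TTSP will be censored at their last date of PS assessment". SAP Appendix 2 (11.2) adds a general statement that patients without an event are censored, but gives no date.

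None of these places mentions death. The SAP does settle death for two other secondary endpoints. It is an event for time to deterioration in quality of life (SAP 6.4.2.5) and is not an event for time to progression (SAP Section 5). SAP 8.9.2.3 tests TTSP with a two-sided log-rank test at 0.05 and reports a hazard ratio.

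**The concern.** A patient who is recorded at ECOG ≥2 and dies before the confirmatory visit has plausibly had the clearest symptomatic progression in the trial, yet the definition does not count it. Death cannot serve as the confirming reading, because the ECOG scale in SAP 6.5.4.1 stops at 4.

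If the default applies, the patient leaves the risk set without an event, at or near the moment of deterioration. Censoring then depends on prognosis, which violates the assumption behind the Kaplan-Meier estimate, the log-rank test and the Cox model. The Kaplan-Meier curve for TTSP is too favourable in any arm where this happens. The comparison between arms is distorted if survival after deterioration differs between them.

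There is also a question of conduct. The trial is open-label and ended early. Without an explicit rule, whoever programs the endpoint could choose how to handle these patients with the outcomes in view.

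**Working it through.** The documents give no TTSP event count, rate or power, so there is no planned figure to reproduce. The check has three parts.

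**1. Trace one patient through the rules.** This is a hypothetical case: ECOG 1 up to Week 12, ECOG 2 at the Week 16 visit (112 days after randomization), death 140 days after randomization, and no PS assessment in between.

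- Event rule: no later visit confirms the reading, so there is no event.
- Rule 1: does not apply, because there are post-baseline ECOG assessments.
- Rule 2: does not apply, because it is for a patient who "has post baseline ECOG assessment but did not have ECOG ≥2 then TTSP will be censored", and this patient did have ECOG ≥2.
- Protocol 10.2.3.2 with SAP 11.2: not confirmed as progressed, so censored at the last PS date, which is the day ECOG 2 was recorded. TTSP = (112 + 1)/30.4375 = 3.71 months, censored.

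If death counted as confirmation, the same patient would be an event at 3.71 months.

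**2. How often could this happen?** Inputs:

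- Confirmation interval: 56 days (SAP 6.4.2.3). The ±7-day visit window (Protocol 9.1) gives 49 to 63 days.
- Days per month: 30.4375 (SAP convention), so 56/30.4375 = 1.84 months.
- Median survival m after first ECOG ≥2: **not in the documents**. It is assumed, with exponential survival, over a range.

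P(death before confirmation) = 1 − 2^(−d/m), with d in months. For m = 3: 1 − 2^(−1.84/3) = 0.346.

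| Assumed median m (months) | 49 days | 56 days | 63 days |
|---|---|---|---|
| 2 | 42.8% | 47.1% | 51.2% |
| 3 | 31.1% | 34.6% | 38.0% |
| 4 | 24.3% | 27.3% | 30.1% |
| 6 | 17.0% | 19.1% | 21.3% |
| 9 | 11.7% | 13.2% | 14.7% |
| 13 | 8.2% | 9.3% | 10.4% |

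**3. What could it do to the comparison?** Suppose both arms reach a first recorded ECOG ≥2 at the same constant rate, and every survivor is confirmed. The rate of counted events in each arm is then that common rate times the share confirmed. With assumed medians of 3 and 6 months, the shares confirmed are 100 − 34.6 = 65.4% and 100 − 19.1 = 80.9%. The apparent hazard ratio is 65.4/80.9 = 0.81, in favour of the arm whose patients die faster, where the true ratio is 1. With equal medians the shares are equal and the apparent ratio is 1. Events are still lost, and the TTSP curves are too high in both arms.

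**The case against.** **The plan does have a default.** Protocol 10.2.3.2 and SAP 11.2 together censor anyone without an event. This is correct, and it means the gap is more than missing detail: following the default produces the informative censoring. A reader might go further and infer that the SAP orders these patients never to count. It does not say so. The list in SAP 6.4.2.3 is incomplete, and the result follows from reading the confirmation condition literally and falling back on the protocol.

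**The two descriptions of the confirming visit might look like a flat contradiction**, because ECOG is scheduled every 4 weeks to Week 24. The documents do not support that reading. ECOG ≥2 is itself progression under Protocol 9.2.20, and Protocol 9.1.2.4 and 9.1.3.5 put visits after progression on an 8-week cycle. The next scheduled visit is therefore normally the 8-week one. Some looseness remains: the synopsis ties the 8-week cycle to Week 24, or to confirmed progression with all allowed treatments given, and extra clinical management visits are permitted. The wordings should be aligned.

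**The size is assumed.** This stands. The planned 9-month control median is survival from randomization, so it does not show that many patients die within 8 weeks of ECOG ≥2. The loss is 13% at an assumed median of 9 months.

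**The confirmation rule does not cause every lost deterioration.** Patients who die before any ECOG ≥2 is recorded are censored under rule 2. That is a separate matter, and the change proposed here would not recover them.

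**The consequences are limited.** TTSP is one of several secondary endpoints. Overall survival and time to deterioration in quality of life both count death. Requiring confirmation is a legitimate choice in itself.

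**Conclusion.** The point holds. SAP 6.4.2.3 does not say how a death between the first ECOG ≥2 and its confirmation is handled, and the default censors the patient at the last PS assessment, often the day of deterioration. The share of first deteriorations affected runs from 47% to 13% for assumed post-deterioration medians of 2 to 9 months. Those figures rest on exponential survival, an 8-week interval and medians that the documents do not give.

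It is tempting to conclude that TTSP will favour whichever arm is doing worse. The documents do not support that. The ratio of 0.81 above requires equal deterioration rates and unequal survival afterwards, and an arm with faster death may also deteriorate faster. The direction of bias in this trial is unknown. The supported conclusion is that the TTSP log-rank test and hazard ratio can be distorted by a rule that is easy to repair. The SAP should be corrected. Overall survival is not affected.

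**What to change.** In SAP 6.4.2.3:

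1. State that a first ECOG ≥2 followed by death before the confirmatory PS assessment is a TTSP event, dated at that first ECOG ≥2.
2. State that a first ECOG ≥2 that is not borne out at the confirmatory assessment, or is left unconfirmed for a reason other than death (withdrawal, loss to follow-up, study termination), is censored at the last PS assessment. Add a sensitivity analysis that counts the unconfirmed readings as events. Separating death from other missing assessments matters here, because early termination may have cut off some confirmatory visits.
3. Keep the 8-week interval and align the reference to the next visit with it, for example as the scheduled PS assessment about 8 weeks after the first ECOG ≥2.
4. List the change in SAP Section 5.

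The cost is one SAP paragraph, some programming and one sensitivity analysis. No new data are needed, because date of death is already collected with the ECOG follow-up (Protocol 9.1.2.4 and 9.1.3.5). The downside is small: a transient ECOG ≥2 in a patient who then dies of another cause would count as an event.

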6.4.2.4 Tumor Response Rate (ORR and DCR)

Tumor Response is based on the radiological tumor assessment performed at specified time points. The post baseline assessments are compared to the baseline assessment and the overall response based on investigator assessment is recorded at each efficacy visit. The tumor response is categorized as Complete Response (CR), Partial Response (PR), Stable Disease (SD) or Progressive Disease (PD). There are three sets of criteria that will be assessed, RECIST 1.1, mRECIST, and EASL.

The best overall response is the best response recorded during the study. It will be determined from the overall responses derived at each efficacy visit using the rules according to the tables in Appendix 3.

The ORR is defined as the proportion of patients achieving a best overall response of confirmed CR, or PR. The disease control rate (DCR) is defined as the proportion of patients achieving a best overall response of confirmed CR, PR, or SD.

Patients who do not have any post baseline tumor assessments for any reason are considered non-responders and are included in the denominator when calculating the response rate.

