#### 9.1.2.3 Q8 WEEKS FOLLOWING RANDOMIZATION TO PROGRESSION

- CT/MR images will be taken as described in Section 9.2.17 for efficacy assessment
- 2. Chest CT/MRI images will be taken every 16 weeks as described in Section 9.2.17.
- Bone scintigraphy for selected patients at week 16 then every 6 months thereafter as described in Section 9.2.17

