#### 9.1.3.5 Q8 WEEKS FOLLOWING PROGRESSION TO DEATH

Every 8 weeks following determination of progression (Section 9.2.20), until death, a clinic visit or telephone follow-up (at the investigator's discretion, if a PS  $\geq$ 2 (symptomatic progression) is assessed and whenever in the best interest of the patient) will be conducted. The following activities will take place:

- ECOG Performance Status (including date of death, if applicable) will be assessed as described in Section 9.2.6.
- 2. Record any treatment and concurrent medications to treat hepatocellular carcinoma and any adverse events as described in Sections 9.2.18, 9.2.19 and 12.3. Medications and therapies used in supportive care will not be recorded.
- 3. Patient Reported Outcome assessments will be obtained as described in Section 9.2.14 at clinic visits

For patients undergoing retreatment procedures, study visits will occur Q8 weeks, until determination of subsequent hepatic progression, during which the procedures described in Sections 9.1.3.3 and 9.1.3.4 will be completed.

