## 9.2.17 Efficacy Imaging – CT/MRI

Baseline efficacy imaging scans will be obtained during screening and efficacy assessment scans will be taken every 8 weeks post randomization until progression is confirmed (see Section 9.2.20). Most patients will be evaluated by CT images. MRI images are also permitted. The imaging modality used at baseline must continue to be used for all efficacy images throughout the study. Triple phase CT will be used in accordance with site standards at baseline for dosimetry determination. SPECT imaging may be performed according to standard of care practices for clinical management but is not a study requirement.

Spiral CT abdomen/pelvis – must be performed with cuts of 10 mm or less in slice thickness contiguously in the axial plane. From these images, hepatic and extra-hepatic lesions will be read.

Spiral CT Chest – must be performed with cuts of 10 mm or less in slice thickness contiguously in the axial plane. From these images, extra-hepatic lesions will be read.

To enable analysis of secondary study endpoints using radiological assessment, investigators will identify, read and use bidimensional measurements of target lesions for size and will record evidence of enhancement and increase in dimension of a pre-existing thrombus for all image timepoints. These data will be captured on the eCRF. Comparison between baseline and subsequent images of quantitative and qualitative findings will determine response according to RECIST v 1.1, mRECIST and EASL which are assessed separately in secondary endpoint analyses.

Bone Scintigraphy – Bone scintigraphy to assess spread of metastatic disease will be performed according to institutional standards. For patients with AFP > 400 ng/mL at screening, results of bone scintigraphy will be recorded at the screening visit and subsequent study visits according to the site standard practice ( week 16 study visit and 6 months thereafter (i.e. months 10, 16, 22, etc.) ). Bone scintigraphy is suggested whenever there is an unjustified increase in AFP or the patient experiences bone pain or symptomatic deterioration and repeated at a frequency according to site standard practice.

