#### 9.2.20 DEFINITION OF PROGRESSION FOR PATIENT MANAGEMENT DECISION-MAKING

For the purposes of this trial, definition of clinical progression for patient management decisions will include assessment of change in PVT status and tumor progression and is defined as:

- Radiological progression as defined by RECIST v 1.1 (after receiving all allowable TheraSphere treatments as specified by the protocol)
  - And/OR
- Development of extra-hepatic disease beyond the limits defined in the eligibility criteria
- Worsening of PVT from baseline defined as change in classification of PVT (per Shi et al) up to Type Illa; Type IIIb or Type IV may not be retreated
- ECOG Performance Status ≥2

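### Best overall response has no cut-off at first progression, and after RECIST 1.1 progression only re-treated TheraSphere patients have scheduled scans on which a later response can be recorded

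*SAP*

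**What the plan says.** **Response rule.** SAP 6.4.2.4 states: "The best overall response is the best response recorded during the study". It is to be derived "using the rules according to the tables in Appendix 3". Those tables give time-point responses only; none ends the count at PD or at re-treatment. The reference stays fixed: "The post baseline assessments are compared to the baseline assessment". On ORR: "The ORR is defined as the proportion of patients achieving a best overall response of confirmed CR, or PR". DCR adds stable disease. SAP 8.9.2.4 compares both rates between arms under RECIST 1.1, mRECIST and EASL.

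**Scanning, both arms.** Protocol 9.2.17: "efficacy assessment scans will be taken every 8 weeks post randomization until progression is confirmed (see Section 9.2.20"). The first item in 9.2.20 is "Radiological progression as defined by RECIST v 1.1 (after receiving all allowable TheraSphere treatments as specified by the protocol"). The other items are extra-hepatic disease, worsening of portal vein thrombosis (PVT) and ECOG 2 or more. PD by mRECIST or EASL is not listed.

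**Control arm.** Protocol 9.1.2.3, which holds the imaging, is headed "Q8 WEEKS FOLLOWING RANDOMIZATION TO PROGRESSION". The post-progression list in 9.1.2.4 contains no imaging, and 9.2.16.3 bars cross-over.

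**TheraSphere arm.** The matching imaging section, 9.1.3.4, has no progression limit in its heading. Protocol 9.1.3.5 adds: "For patients undergoing retreatment procedures, study visits will occur Q8 weeks, until determination of subsequent hepatic progression", with the procedures of 9.1.3.3 and 9.1.3.4, which include CT/MR. However, the treatment-arm schedule (protocol 3.2, repeated in SAP 6.1) marks no CT in the follow-up column.

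**The concern.** A best response is a maximum over the assessments made. If one arm is assessed longer, and is re-treated during the extra time, its maximum can rise but cannot fall. Under this plan a TheraSphere patient can be a time-to-progression event at first PD and later become a responder. A control patient with RECIST PD has no scheduled scan on which the same could be recorded.

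At stake are the ORR and DCR comparisons under three criteria. They are investigator-assessed in an open-label trial (SAP 4.3) and carry no multiplicity adjustment (SAP 7.6). Part of any observed difference could come from the scan schedule and post-progression re-treatment rather than from response up to progression. Overall survival is not affected.

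**Working it through.** **Step 1: does the asymmetry follow from the text?**

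| | Control | TheraSphere, re-treated after PD |
|---|---|---|
| Scheduled CT/MR after first RECIST PD | None (9.1.2.3, 9.1.2.4, 9.2.17) | Every 8 weeks until the next hepatic progression (9.1.3.5) |
| Route to re-treatment with TheraSphere | None; cross-over barred (9.2.16.3) | Allowed, up to three administrations in total (9.2.16.1.1, 9.2.16.3) |
| Cut-off on best overall response | None | None |

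The rule is the same for both arms, but it has extra assessments to work on in only one of them. For ORR it can add patients with no earlier CR or PR. For DCR it can add mainly those whose first scan was already PD, since others would normally have recorded at least stable disease before progressing.

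**Step 2: what could the size be?** The documents give no expected ORR or DCR, re-treatment rate, response rate after re-treatment, or final sample size after early termination. There is therefore no figure of the plan's own to reproduce, and every input below is an assumption:

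- p = true ORR up to first PD, equal in both arms: 10%
- q = share of TheraSphere non-responders re-treated after PD: 10-30%
- r = share of those who then reach CR or PR: 10-40%
- n = 40 or 80 per arm

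Formula: TheraSphere ORR = p + (1 − p) × q × r.

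- Low end: 0.10 + 0.90 × 0.10 × 0.10 = 0.109
- High end: 0.10 + 0.90 × 0.30 × 0.40 = 0.208

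The false-significance rate is the exact binomial probability that the 95% continuity-corrected Newcombe-Wilson interval for the difference excludes zero in either direction. It is obtained by enumerating all pairs of responder counts.

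| q | r | TheraSphere ORR | n = 40 per arm | n = 80 per arm |
|---|---|---|---|---|
| 0 | n/a | 10.0% | 1.7% | 2.8% |
| 10% | 10% | 10.9% | 1.9% | 3.2% |
| 10% | 30% | 12.7% | 2.9% | 5.4% |
| 20% | 40% | 17.2% | 9.2% | 20.7% |
| 30% | 30% | 18.1% | 11.2% | 25.3% |
| 30% | 40% | 20.8% | 18.6% | 41.1% |

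Without the effect the rate lies below the nominal 5%, because the continuity correction is conservative at these sizes. With few patients re-treated and few responding, it stays below 5% even with the effect.

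**Step 3: with the cut-off.** If only assessments up to first PD count in both arms, the q × r term disappears and the excess from this rule is zero.

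**The case against.** **The upper rows presume a strong effect of re-treatment.** A 30-40% response after progression is three to four times the assumed first-line 10%, in patients who had not responded and still measured against baseline. If r equals 10% and q is 30%, TheraSphere ORR is 12.7% and the false-significance rate is 2.9% or 5.4%. This stands.

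**The protocol and SAP contain brakes.** These also stand, and they push towards the low end:

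- ORR requires a confirmed response, although Appendix 3 gives no confirmation rule.
- Re-treated patients must again meet the initial eligibility criteria (9.2.16.1.1).
- Re-treatment of multifocal progression requires an earlier RECIST CR or PR (9.2.16.3), so it adds little or nothing to RECIST ORR.
- Any visit with a new lesion is PD (Appendix 3).

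They do not close the gap. Re-treatment of a previously treated tumour that progresses carries no prior-response condition, and confirmation could itself fall on scans after re-treatment.

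**The schedule table shows no CT in follow-up.** This is true, and it conflicts with 9.1.3.5. The two must be reconciled. The point rests on the text of 9.1.3.5.

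**Stronger readings a reader might infer, which the documents do not support:**

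- *Only TheraSphere patients are scanned past progression under all three criteria.* This is exact for scheduled scans after RECIST 1.1 PD only. Because 9.2.20 uses RECIST, either arm may be scanned past an mRECIST or EASL PD that is not a RECIST PD; the re-treatment asymmetry comes on top. Exit imaging as appropriate (9.1.4) applies to both arms.
- *Time to PVT worsening and time to progression are biased the same way.* These are first-event endpoints with censoring. Longer observation does not by itself bias a log-rank test, and it can only reveal more events in the TheraSphere arm. No direction or size in favour of TheraSphere is shown.
- *Every response after a repeat administration is suspect.* Further administrations without radiological progression are part of the assigned regimen (9.1.3.2, 9.2.16.1.1).

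**Conclusion.** The point holds for ORR and DCR. The response rule has no cut-off at first PD, and post-progression re-treatment with continued scanning exists in one arm only. The direction is fixed: the rule can add responders or disease control for TheraSphere and cannot remove any.

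The size is not known. It is zero if nobody first responds, or first reaches stable disease, after PD and re-treatment. Under the assumed ranges TheraSphere ORR moves from 10% to 11-21%. The false-significance rate is 1.9-19% at 40 per arm and 3.2-41% at 80 per arm, against 1.7% and 2.8% without the effect. A reader might take the upper figures as the expected inflation; the documents support neither the rates nor the sample sizes behind them, and the low end is more consistent with the protocol's own restrictions.

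These are secondary endpoints in a trial that stopped early, but the comparisons are still planned and the correction is simple, so it should be made.

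**What to change.** In SAP 6.4.2.4, for both arms and separately for RECIST 1.1, mRECIST and EASL:

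1. Define best overall response as the best time-point response from randomisation up to first PD by that criterion and before any post-progression anti-cancer therapy, including TheraSphere given after PD. Any confirming assessment must fall in the same window.
2. State that responses after TheraSphere administrations given without progression still count.
3. Report responses after post-progression re-treatment separately and descriptively, with no between-arm test.
4. State the confirmation rule, which Appendix 3 lacks.

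Reconcile protocol 9.1.3.5 with the follow-up column of the treatment-arm schedule, so that it is clear which scans were planned.

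**Cost.** Items 1 to 4 need SAP wording and derivation changes only; no new data are required. TheraSphere ORR and DCR may come out lower, by an amount that depends on how many patients respond only after re-treatment.
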